4.2.5.3 Handling of Dropouts and Missing Data

No data imputation.

4.2.5.4 Primary Analysis of Secondary Endpoint

The number and proportion of participants with $\geq 50\%$ reduction from baseline in daily maintenance OCS dose are summarised using the same approach described for the primary endpoint (Section 4.2.1.4) on the FAS.

4.2.5.5 Additional Analyses of Secondary Endpoint

No additional analysis.

4.2.5.6 Subgroup Analyses of Secondary Endpoint

The analysis described in Section 4.2.5.4 is repeated in subgroups described in Section 4.2.1.7.

4.2.5.7 Interim Analysis of Secondary Endpoint

The derivation of baseline, post-baseline and change from baseline in daily maintenance OCS dose is described in Section 4.2.7.2.

The number and proportion of participants with $\geq 50\%$ reduction from baseline in daily maintenance OCS dose is summarised over time on the FAS.

4.2.6 Secondary Endpoint - Categorised percent reduction from baseline in the daily maintenance OCS dose at Week 28 and Week 52.

4.2.6.1 Definition

The proportion of participants for each reduction categories from baseline in the daily maintenance OCS dose are calculated at Week 28 and Week 52.

4.2.6.2 Derivations

The percentage reduction from baseline in daily maintenance OCS dose at Week 28 and at Week 52 whilst maintaining asthma control is calculated as described in Section 3.3 and categorised as follows:

- Category 1: $\geq 90\%$ to $\leq 100\%$ reduction
- Category 2: $\geq 75\%$ to $\leq 90\%$ reduction
- Category 3: \geq 50% to <75% reduction
- Category 4: >0% to <50% reduction
- Category 5: no change or any increase.

The baseline and final daily maintenance OCS dose derivation are defined in Sections 3.3.1.1 and 4.2.1.2.

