because of loss of asthma control and/or evidence of AI, as measured by cortisol levels (morning cortisol level or adrenocorticotropic hormone [ACTH] stimulation test).

Table A Oral Corticosteroid Titration Schema Until Reaching 5 mg/day

Baseline OCS dose	OCS down-titration schema until reaching 5 mg/day (without worsening of asthma)
> 20 mg/day	Reductions of 5 mg of the daily dose every 1 week until reaching a dose of 20 mg/day; followed by reductions of 5 mg every 2 weeks (Q2W) until a dose of 10 mg/day is reached; followed by reductions of 2.5 mg Q2W until reaching a dose of 7.5 mg/day; and then reductions of 2.5 mg Q4W until reaching a dose of 5 mg/day
> 10 to ≤ 20 mg/day	Reductions of 5 mg of the daily dose Q2W until reaching a dose of 10 mg/day; followed by reductions of 2.5 mg Q2W until reaching a dose of 7.5 mg/day; and then reductions of 2.5 mg Q4W until reaching a dose of 5 mg/day
> 7.5 to ≤ 10 mg/day	Reductions of 2.5 mg of the daily dose Q2W until reaching a dose of 7.5 mg/day followed by reductions of 2.5 mg Q4W until reaching a dose of 5 mg/day
> 5 to ≤ 7.5 mg/day	Reductions of 2.5 mg of the daily dose Q4W until reaching a dose of 5 mg/day

Abbreviations: OCS = oral corticosteroids; Q2W = every two weeks; Q4W = every four weeks.

Once a participant reaches the lowest stable dose, the participant will be considered in maintenance. From Week 48 to Week 52, all participants will remain on their stable daily OCS dose, except if an asthma deterioration or exacerbation occurs. No further down-titration will be allowed from Week 48 onwards.

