- 2. **Induction phase From Week 0 to 4:** After confirmation of eligibility criteria, participants will start receiving tezepelumab treatment at Visit 2/Week 0 (baseline) and should remain stable on their baseline OCS dose during this phase.
- 3. Oral corticosteroid reduction and maintenance phase From Week 4 to Week 52: Site visits will occur Q4W. Participants will reduce their dosage of OCS according to the schema defined in Table 7 for each baseline OCS dose until they reach the lowest stable OCS dose or until Week 48. The first OCS dose reduction may occur at Visit 3. OCS dose reduction may occur remotely if the scheduled dose reduction does not coincide with a site visit.

Participants will be considered as having reached the lowest stable dose when they have discontinued OCS or no further OCS reduction is possible because of loss of asthma control and/or evidence of AI (as confirmed by morning cortisol test or adrenocorticotropic hormone [ACTH] stimulation test).

Once they reach the lowest stable dose, participants will be considered in maintenance. From Week 48 to Week 52, all participants will remain on their stable daily OCS dose, except if an asthma deterioration or exacerbation occurs. No further down-titration will be allowed from Week 48 onwards.

HPA axis integrity will be evaluated for all participants who have been on 5 mg/day OCS for 4 weeks and prior to any further tapering down the OCS dose (for participants with baseline OCS doses equal to 5 mg/day, this will be assessed 4 weeks after the first dose of tezepelumab administration and before initiation of the OCS reduction and maintenance phase). A screening method with morning serum cortisol (see Section 8.2.1.1) will be done (8 to 9 am morning cortisol level), to evaluate whether the participant has normal cortisol levels or complete AI. Cortisol levels from the morning cortisol test that will be below normal range and above the complete AI range will be considered 'indeterminate' and will require additional testing (ACTH stimulation test or alternative method, as described in Appendix M).

Depending on the morning cortisol level results, the participant will continue per the following guidance:

- Cortisol levels within normal range (Table 9):
 - Participant exhibits absence of signs and/or symptoms of AI: continue OCS down-titration by 2.5 mg Q4W
 - Participant exhibits signs and/or symptoms of AI: continue OCS down-titration at a slower pace (1 mg Q4W)

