5.1 Inclusion Criteria

Participants are eligible to be included in the study only if all of the following criteria apply:

Age

1 Participant must be 18 to 80 years of age inclusive, at the time of signing the informed consent.

Type of Participant and Disease Characteristics

- History of physician diagnosed asthma that requires continuous treatment with high-dose ICS (high-dose ICS is the highest approved dose in a country; see Appendix I) plus a LABA for at least 6 months prior to Visit 1 (to be documented in medical records). The ICS and LABA can be contained within a combination product or given by separate inhalers:
 - (a) For ICS/LABA combination preparations, the highest approved maintenance dose in the local country will meet this ICS criterion.

Note: Additional maintenance asthma controller medications (eg, LTRAs, tiotropium, cromone, theophylline) are allowed (see Table 5).

- 3 Long-term OCS therapy for asthma, equivalent to a daily dose of at least 5 mg and up to 40 mg of prednisone/prednisolone for at least 3 continuous months directly preceding Visit 1 (to be documented in medical records).
 - Note: Alternate intake of OCS (ie, every other day) or other frequency is allowed provided the average daily dose is equivalent to at least 5 mg of prednisone/prednisolone and the participant is switched to a daily intake of prednisone/prednisolone at Visit 1. Systemic corticosteroid doses administered by any route other than oral cannot be used to determine the average daily dose preceding Visit 1.
- 4 Participant should be on a stable maintenance OCS dose for at least 4 weeks prior to Visit 1. If taking a type of OCS other than prednisone/prednisolone at Visit 1, then the participant must agree to switch to prednisone/prednisolone as their OCS by Visit 2 and for the duration of the study.

- Documented history of at least 1 asthma exacerbation event within 12 months prior to Visit 1. An asthma exacerbation will be defined as a worsening of asthma symptoms that leads to any of the following:
 - (a) A temporary bolus/burst of systemic corticosteroids (or a temporary increase in stable OCS background dose) for at least 3 consecutive days to treat symptoms of asthma worsening; a single depo-injectable dose of corticosteroids will be considered equivalent to a 3-day bolus/burst of systemic corticosteroids

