9.4.3.2 Secondary Endpoints

The following outcomes are designed to support the secondary objectives of the study:

- Rate of annualised asthma exacerbation (all exacerbations; exacerbations associated with hospitalisation or ER visit, and exacerbation associated with hospitalisation only) at Week 28 or Week 52
- Proportion of participants who did not experience an exacerbation over 28 or 52 weeks
- Proportion of participants who did not experience an exacerbation associated with hospitalisation or ER visit over 28 or 52 weeks
- Proportion of participants who did not experience an exacerbation associated with hospitalisation over 28 or 52 weeks
- Proportion of participants with ≥ 50% reduction from baseline in daily maintenance OCS dose at Week 28 or Week 52
- Proportion of participants for each pre-specified categories of percentage reduction from baseline in daily maintenance OCS dose at Week 28 or Week 52:
 - \geq 90% to \leq 100% reduction; \geq 75% to < 90% reduction; \geq 50% to < 75% reduction; > 0% to < 50% reduction; no change or any increase.
- Mean change from baseline over time in:
 - percentage reduction from baseline in daily maintenance OCS dose
 - post-BD FEV₁
 - ACQ-6 scores
 - AQLQ(s)+12 total scores
 - SGRQ total scores.

The number and proportion (with 95% CI) of participants who remained exacerbation free, those who did not experience an exacerbation associated with hospitalisation or ER visit or with hospitalisation only, reduced the OCS as per predefined categories, and those defined as responders (based on ACQ-6, AQLQ(s)+12 or SGRQ total scores) will be summarised using the same approach as for the primary endpoint.

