To assess the ability of tezepelumab 210 mg SC to allow reduction of the prescribed OCS dose without loss of asthma control ^a	 Proportion of participants with ≥ 50% reduction from baseline in daily maintenance OCS dose at Week 28 and Week 52 Categorised percent reduction from baseline in the daily maintenance OCS dose (categories: ≥ 90% to ≤ 100% reduction, ≥ 75% to < 90% reduction, ≥ 50% to < 75% reduction, > 0% to < 50% reduction, no change or any increase) at Week 28 and Week 52 Absolute and percent change from baseline in daily maintenance OCS dose at Week 28 and Week 52 		
To assess the ability of tezepelumab to improve lung function	Change from baseline in post-BD FEV ₁ at Week 28 and Week 52		

To assess the ability of tezepelumab to improve asthma control ^a	Change from baseline in Asthma Control Questionnaire 6 (ACQ-6) at Week 28 and Week 52
To assess the ability of tezepelumab to improve asthma related quality of life	Change from baseline in standardised Asthma Quality of Life Questionnaire for 12 years and older (AQLQ[s]+12) total score at Week 28 and Week 52
	Change from baseline in St. George's Respiratory Questionnaire (SGRQ) total score at Week 28 and Week 52
Safety objective	
To describe the safety and tolerability of tezepelumab	Serious adverse events (SAEs), discontinuation of investigational product due to an adverse event (DAEs), and adverse events of special interest (AESI)
Exploratory objectives	
To describe changes from baseline in biomarker levels	Change from baseline in biomarker levels at Week 28 and Week 52
To assess the ability of tezepelumab 210 mg SC to allow reduction of the prescribed OCS dose without loss of asthma control ^a	Time to 50% reduction of OCS dose at Week 28 and Week 52
	Time to 100% reduction of OCS dose at Week 28 and Week 52
To describe the occurrence of AI	Proportion of participants with normal, partial, complete AI at Week 28 and Week 52
To assess the ability of tezepelumab to improve asthma control ^a	Proportion of ACQ-6 responders at Week 28 and Week 52
To assess the ability of tezepelumab to improve asthma related quality of life	Proportion of AQLQ(s)+12 responders at Week 28 and Week 52
	Proportion of SGRQ responders at Week 28 and Week 52
To describe the ability of tezepelumab to improve Asthma Impairment and Risk	Change from baseline in AIRQ at Week 52
Questionnaire (AIRQ TM)	• Proportions of AIRQ responders at Week 52

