2 CHANGES TO PROTOCOL PLANNED ANALYSES

No difference with the most recent version of the CSP.

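### As printed, SAP 4.2.6.2 closes Category 2 at ≤90%, so a reduction of exactly 90% meets two categories and contradicts SAP Table 1 and the protocol

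*SAP*

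**What the plan says.** SAP 4.2.6.2 lists five categories of percent reduction from baseline in daily maintenance OCS dose. The first two are "Category 1: $\geq 90\%$ to $\leq 100\%$ reduction" and "Category 2: $\geq 75\%$ to $\leq 90\%$ reduction". Both include 90%. The remaining boundaries in the list (75%, 50%, 0%) do not overlap, and neither 4.2.6.2 nor 4.2.6.4 gives a tie-break.

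The same endpoint is stated elsewhere with an open upper limit for the second category:

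- SAP 1.1, Table 1: "≥ 75% to < 90% reduction".
- Protocol 9.4.3.2: "\geq 75% to < 90% reduction". The protocol synopsis and Protocol Section 3, Table 2 agree.

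SAP Section 2 states: "No difference with the most recent version of the CSP". The closed limit in 4.2.6.2 is therefore not a declared change.

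**The concern.** The derivations section is where a programmer looks for the operative rule. Taken literally, this rule gives categories that are not mutually exclusive. Someone at exactly 90% could be counted in both rows, so that the percentages exceed 100%, or could be placed in Category 2 and leave the top row.

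The top row matters to readers because Protocol 2.1 cites the same ≥90% measure from the earlier placebo-controlled OCS-reduction trial of tezepelumab (54.1% versus 46.1%). OCS doses move in discrete steps, so a round value such as 90% may well be hit exactly. The table is also repeated in the subgroups of SAP 4.2.1.7.

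**Working it through.** The plan gives no figure for this boundary. Its one design figure, 5.8 percentage points either side of 50% with 300 participants (SAP 1.3), reproduces with exact Clopper-Pearson limits and plays no part here.

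**Step 1: the overlap.** Category 1 is the closed interval from 90 to 100. Category 2 in 4.2.6.2 is the closed interval from 75 to 90. They share the single point 90. With Category 2 ending below 90, the five categories are exclusive and exhaustive.

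**Step 2: can exactly 90% occur at Week 28?** Inputs:

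- Entry dose: "equivalent to a daily dose of at least 5 mg and up to 40 mg of prednisone/prednisolone" (Protocol 5.1).
- Start of taper: "The first OCS dose reduction may occur at Visit 3", that is, Week 4 (Protocol 4.1).
- Above 20 mg: "Reductions of 5 mg of the daily dose every 1 week until reaching a dose of 20 mg/day" (Protocol 1.1). Then 5 mg every 2 weeks to 10 mg, 2.5 mg after 2 weeks to 7.5 mg, and 2.5 mg after 4 weeks to 5 mg.
- Four weeks at 5 mg, then HPA testing, with about 1 week more if the ACTH test is needed (Protocol 4.1).
- Below 5 mg: 1 mg every 4 weeks with partial AI or AI symptoms; 2.5 mg every 4 weeks without AI (Protocol 4.1, Table 7).
- Final dose: the last dose unchanged for at least 2 weeks (SAP 4.2.1.2, Table 4).

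Reduction = (baseline − final) / baseline × 100. On the 1 mg path with a 1-week test delay:

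| Entry dose (mg) | 5 mg reached | Later steps (week: dose in mg) | Stable dose at Week 28 | Reduction |
|---|---|---|---|---|
| 10 | Week 8 | 13: 4, 17: 3, 21: 2, 25: 1 | 1 mg | (10 − 1)/10 = 90.0% |
| 20 | Week 12 | 17: 4, 21: 3, 25: 2 | 2 mg | (20 − 2)/20 = 90.0% |
| 30 | Week 15 | 20: 4, 24: 3, 28: 2 | 3 mg (2 mg only just started) | (30 − 3)/30 = 90.0% |
| 40 | Week 17 | 22: 4, 26: 3 | 3 mg | (40 − 3)/40 = 92.5% |

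With no test delay, each step below 5 mg comes a week earlier. The stable doses for 10, 20 and 30 mg entrants are unchanged, because the next step has then lasted at most 1 week by Week 28.

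**Step 3: how robust is this to timing?** Two waits before the 7.5 to 5 mg step (2 or 4 weeks), three test delays (0, 7, 14 days) and 11 visit days (Day 197 ± 5) give 2 × 3 × 11 = 66 scenarios per entry dose. On the 1 mg path, exactly 90% occurs in 55 of 66 for 10 mg, 55 of 66 for 20 mg, 48 of 66 for 30 mg and 15 of 66 for 40 mg. It occurs in none for 5, 7.5, 12.5, 15, 17.5, 25 or 35 mg. On the uninterrupted path without AI it occurs for no entry dose; nearly all are at 0 mg. These are counts of timing scenarios, not probabilities.

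**Step 4: does rounding separate the categories?** No. In floating-point arithmetic (1 − 10)/10, (2 − 20)/20 and (3 − 30)/30, each times 100, all return exactly −90.0.

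**Step 5: consequence.** Let s be the share of the Full Analysis Set at exactly 90%.

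- Independent flags for each category: the rows sum to 100% + s.
- One variable, Category 1 tested first: no error.
- One variable, Category 2 tested first or overwriting: the top row loses s and Category 2 gains s.

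The documents do not give s. Purely as illustration, s = 5% would be 0.05 × 300 = 15 participants and a total of 105%; s = 10% would be 30 participants and 110%.

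**The case against.** The strongest reply is that the sign may not be real. The text reviewed was machine-read from PDF, Categories 3 and 4 in the same list carry a plain <, and the other statements of the endpoint have <90%. A misread < cannot be excluded. This stands, and it makes the point conditional on checking the page.

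Second, the intended rule is not in doubt: SAP Table 1 and the protocol give it, and a programmer working from either would code it correctly. That also stands. It leaves the derivation line contradicting them, but it makes this a one-character slip rather than a choice of analysis.

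Third, exactly 90% is confined to particular paths. Under Protocol Table 7, a participant whose 2-month repeat test is normal while on 3 mg or less may go straight to 0 mg and so miss 90%. Where only 5 mg tablets exist, Appendix E delivers 1.25 mg for a target of 1 mg and 2.5 mg for a target of 2 or 3 mg. If recorded that way, the 10, 20 and 30 mg entrants show 87.5%, 87.5% and 91.7%. On the uninterrupted 1 mg path with the 1-week delay these entrants reach 0 mg at Weeks 29, 33 and 36, so Week 52 is not affected on that path. All of this narrows the group at 90% without emptying it; interrupted tapers were not enumerated.

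A reader might infer that the ≥90% row is wrongly defined, or that it will move by 5 to 10 points and spoil comparison with the earlier trial. The documents do not support that. Category 1 is itself defined correctly in 4.2.6.2, and code that tests categories in the listed order puts 90% where it belongs. A shift of that size would need both an unsourced share of participants at exactly 90% and an adverse coding choice.

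**Conclusion.** Wrong as written, minor. On the text as supplied, the derivation makes Categories 1 and 2 overlap at 90% and contradicts SAP Table 1 and the protocol; that much needs no assumption beyond the sign being ≤. Exactly 90% is attainable at Week 28 for entrants at 10, 20 or 30 mg who remain on the 1 mg every-4-weeks path, and less often at 40 mg. It is not attained on the uninterrupted path without AI.

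The share affected is unknown, so no size can be put on the effect. It would be wrong to read this as a common value across the trial: it depends on entry dose, adrenal status, timing and how tablet doses are recorded. One descriptive secondary endpoint and its subgroup tables are at risk. The primary endpoints, the ≥50% reduction endpoint and the sample size do not use this boundary, and no hypothesis is tested.

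**What to change.** Check the sign on the original SAP page. If it is ≤, change Category 2 in SAP 4.2.6.2 to ≥75% to <90% reduction, so that exactly 90% falls only in Category 1 and the line agrees with SAP Table 1 and the protocol. If it is already <, no change is needed.

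The cost is one character, with no analytical downside. If tables have already been programmed, confirm that the code assigns 90% to Category 1 and that the rows sum to 100% apart from any missing data. The same edit could correct the cross-reference in 4.2.6.2, which points to 3.3.1.1 (study periods) for the baseline dose; the baseline definition is in 3.3.1.2.

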4.2.6.3 Handling of Dropouts and Missing Data

No data imputation.

4.2.6.4 Primary Analysis of Secondary Endpoint

The number and proportions of participants in each categorised percent reduction from baseline in the final daily maintenance OCS dose at Week 28 and Week 52 are summarised using the same approach described for the primary endpoint (Section 4.2.1.4) on the FAS.

4.2.6.5 Additional Analyses of Secondary Endpoint

No additional analysis.

4.2.6.6 Subgroup Analyses of Secondary Endpoint

The analysis described in Section 4.2.6.4 is repeated in subgroups described in Section 4.2.1.7.

4.2.6.7 Interim Analysis of Secondary Endpoint

No presentation for interim analysis.

4.2.7 Secondary Endpoint - Absolute and percent change from baseline in daily maintenance OCS dose at Week 28 and Week 52.

4.2.7.1 Definition

The absolute and percent changes from baseline in the daily maintenance OCS dose are calculated at Week 28 and Week 52.

4.2.7.2 Derivations

The daily OCS dose at Visit X is the latest OCS dose during this visit. Note the visit windows for daily OCS dose per visits are based on actual visit dates as described in Section 3.3.2.

The absolute and percent change from baseline in daily OCS dose at a post-baseline visit is calculated as defined in Section 3.3 on the FAS. The baseline daily maintenance OCS dose derivation is defined in Section 3.3.1.2. The derivation of daily OCS dose at a post-baseline visit is defined in Section 4.2.1.2.

The data selected for the analysis are described in Section 4.2.1.2.

4.2.7.3 Handling of Dropouts and Missing Data

No data imputation.

4.2.7.4 Primary Analysis of Secondary Endpoint

The absolute values as well as absolute and percent change from baseline in daily maintenance OCS dose is summarised using descriptive statistics over time on the FAS. All data available at primary DBL is presented, which includes data beyond Week 28 (see Section 3.1).

The percent change from baseline in daily maintenance OCS dose is analysed using a model for repeated measures. The percent change from baseline at each post-baseline visit up to and including Week 28 (Week 52 for the Week 52 analysis) is the dependent variable in the model. The visit is included as a categorical covariate and the OCS dose at baseline and logarithm of baseline blood eosinophils count are included as continuous covariates in the model. The analysis is performed on participants in the FAS who have an OCS baseline and at least one non-missing post baseline value. Participant is included in the model using the REPEATED statement (no RANDOM statement is specified). The variance-covariance

matrix is assumed to be unstructured. If the model does not converge, then compound symmetry matrix is used. The Kenward-Roger approximation to estimating the degrees of freedom is used for tests of fixed effects derived from the model.

The adjusted mean changes from baseline together with its 95% CI are estimated from this model, tabulated and presented graphically over time.

The relation between the percent change from baseline in daily maintenance OCS dose at Week 28 (Week 52) and each continuous baseline biomarker variable separately (EOS, FeNO, and total IgE) is estimated following nonparametric approach such as a locally estimated scatterplot smoothing (LOESS) plot or a generalized additive model (GAM). The model-based percent change from baseline at Week 28 (Week 52) is presented together with 95% confidence band on the graphs against the baseline biomarker variable.

